12.6.5 Electrocardiogram (ECG)

The collected ECG values will be listed.

12.6.6 Total Acetaminophen (Rescue Medication) Dose

The number and percentage of participants taking acetaminophen between baseline (Study VMDN-003-2) and up to but not including Day 270, Day 270 and up to but not including Day 365 and baseline (Study VMDN-003-2) and up to but not including Day 365 will be calculated by the treatment group. The number and percentage of participants taking acetaminophen between baseline (Study VMDN-003-2) and Day 270, Day 270 and Day 365 and baseline (Study VMDN-003-2) and Day 365 will be summarized by the treatment group. The mean, standard deviation, minimum, maximum, median, and 1st and 3rd quartiles of days to the first start date of the acetaminophen will be summarized by the treatment group using observed data; participants not taking acetaminophen will not be included in these descriptive statistics. The total dose of acetaminophen of each participant between baseline (Study VMDN-003-2) and Day 270, Day 270 and Day 365 and baseline (Study VMDN-003-2) and Day 365 will be summarized by the treatment group. These analyses will be based on the ITT and PP population.

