9.3.3. Exploratory Efficacy Endpoints

Exploratory efficacy endpoints include:

- Patient Global Impression of Change (PGIC) on Day 270 and Day 365 for Engensis compared to Placebo
- Proportion of Responders (≥ 50% reduction in the ADPSs from the full BPI-DPN) during the 7 days prior to the Day 270 Visit and the 7 days prior to the Day 365 Visit who were Responders on Day 104 (final injection visit in Study VMDN 003 2) for Engensis compared to Placebo
- Change in the BST from the Day 0 Visit (Study VMDN 003-2) to Day 270 and to Day 365 Visit for Engensis compared to Placebo

Version 1.0 48 Final: 11 Feb 2021

 Proportion of Responders (≥ 20, 30, 40, 60, and 70% reduction in the ADPSs from the full BPI-DPN) from the 7 days prior to the Day 0 Visit (Study VMDN 003-2) to the 7 days prior to the Day 270 Visit and the 7 days prior to the Day 365 Visit for Engensis compared to Placebo

- Change in the means of the ADPSs from the full BPI-DPN from the 7 days prior to the Day 0 Visit (Study VMDN-003-2) to the 7 days prior to the Day 270 Visit for Engensis compared to Placebo
- Changes in the severity scores (from the full BPI-DPN) from the 7 days prior to the Day 0 Visit (Study VMDN-003-2) to 7 days prior to the Day 270 Visit and to 7 days prior to the Day 365 Visit for Engensis compared to Placebo
- Changes in MNSI assessments from the Day 0 Visit (Study VMDN 003 2) to Day 270 and Day 365 for Engensis compared to Placebo
- Changes in the SF-36 from the Day 0 Visit (Study VMDN 003 2) to Day 270 and to Day 365 for Engensis compared to Placebo
- Changes in the EQ-5D from the Day 0 Visit (Study VMDN-003-2) to Day 270 and to Day 365 for Engensis compared to Placebo
- Changes in the means of the daily use of rescue medication from the Day 180 Visit (Study VMDN-003-2) to Day 270 and to Day 365 for Engensis compared to Placebo

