9.0 Population Sets

9.1 Intent-to-Treat (ITT) Population

This subset includes all enrolled Participants in this study who start this extension study at the Day 180 Visit (Study VMDN-003-2). Participants in the ITT population will be analyzed according to original treatment assignment in Study VMDN-003-2, regardless of actual treatment received. The primary analyses of the primary and secondary efficacy endpoints will be based on this ITT population.

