9.4 Per Protocol (PP) Populations

The Per Protocol population is a subset of mITT. It includes all mITT participants who meet all of the following criteria for Study VMDN-003-2 and Study VMDN-003-2b:

- The participant meets major protocol eligibility criteria determined by Clinical Data Review Committee (CDRC) prior to database lock and breaking the randomization codes.
- The participant received all 32 injections from each visit (Day 0, Day 14, Day 90 and Day 104) in Study VMDN-003-2, based on the randomized treatments and had a Day 365 Visit, including a 7-day ADPS (with at least 5 of 7 days of BPI-DPN eDiary collected prior to Day 365 Visit).

The CDRC, which is blinded to the treatment information of each participant, may determine additional criteria, if any, before unblinding the randomization code.

The PP population will be used in the sensitivity analyses for the primary and secondary efficacy endpoints.

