10.6.2 Addressing Missing Data for the Secondary and Exploratory Efficacy

Missing individual item scores of the full BPI-DPN will be imputed for the calculation of the average score within a domain using the average score across the non-missing items within the domain at a subject's visit provided that the proportion of missing items scores within that domain is less than 25%; otherwise, the domain score at that visit is missing.

The same method as the full BPI-DPN will be used when addressing the missing data for SF-36 and EQ-5D.

Individual item scores on the MNSI (both physical assessment and history) questionnaire will not be imputed. The total MNSI scores will be imputed using a "worst-case" imputation approach. Missing individual items will be imputed as the category corresponding to the largest number of points in the total score calculation. This equates to a response of "Yes" to questions 1-3, 5-6, 8-9, 11-12, and 14-15 and "No" to questions 7 and 13 on the history assessment. On the physical assessment, it equates to a response of "No" on the "Appearance of Feet" question, a response of "Present" on the "Ulceration" question, and a response of "Absent" on the "Ankle Reflexes", "Vibration perception at great toe", and "Monofilament" questions.

Missing PGIC and BST scores and the use of rescue medication will not be imputed.

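### SAP 12.6.6 totals rescue acetaminophen without dividing by days observed and times first use among users only, so the ITT totals depend on length of follow-up and the timing statistic can hide a difference

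*SAP*

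**What the plan says.** SAP 12.6.6 describes rescue acetaminophen by treatment group in three ways.

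- **Incidence.** It reports "The number and percentage of participants taking acetaminophen between baseline (Study VMDN-003-2) and up to but not including Day 270", and the same for Day 270 to Day 365 and baseline to Day 365. Non-users stay in the denominator.
- **Time to first use.** Days to the first start date are summarised from observed data, and "participants not taking acetaminophen will not be included in these descriptive statistics".
- **Amount.** It summarises "The total dose of acetaminophen of each participant between baseline (Study VMDN-003-2) and Day 270", and the same for the other two windows. No divisor is given, and there is no rule for a participant who leaves inside a window.

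On the analysis sets, "These analyses will be based on the ITT and PP population". SAP 9.1 defines ITT: "This subset includes all enrolled Participants in this study who start this extension study at the Day 180 Visit (Study VMDN-003-2"). SAP 9.4 limits PP to participants who received all injections "based on the randomized treatments and had a Day 365 Visit, including a 7-day ADPS". On missing data, SAP 10.6.2 says "Missing PGIC and BST scores and the use of rescue medication will not be imputed".

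SAP 12.6 makes the whole section descriptive, without formal testing, and restricts it to extension-study data. The windows in 12.6.6 nevertheless begin at main-study baseline.

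Protocol 9.3.3 lists a per-day exploratory efficacy endpoint: "Changes in the means of the daily use of rescue medication from the Day 180 Visit (Study VMDN-003-2) to Day 270", and to Day 365. Protocol 6.4 has rescue use recorded daily in the eDiary, so a per-day denominator can be built.

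**The concern.** A total mixes how much a participant takes per day with how long that participant is followed. Two people with the same daily use have different totals if one leaves early. If the arms lose participants at different rates or times, or if leaving is related to rescue use, the ITT totals differ for reasons other than daily use.

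The users-only timing statistic has a different weakness. It averages over people selected by what happened after randomisation. If treatment delays first use beyond the end of follow-up, the participants who benefit most drop out of the average.

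Acetaminophen is the permitted rescue for neuropathic pain (Protocol 6.2.1). The visible primary model (SAP 12.5.1) has no term for it, and the medication sensitivity analysis (SAP 12.5.1.1) covers prohibited drugs only. A reader who wants to know whether rescue use was similar in the two arms will therefore look at these tables.

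**Working it through.** The plan states no figure for rescue use, so there is none to reproduce. The windows and analysis sets come from SAP 9.1, 9.4 and 12.6.6. Dropout rates, daily use and first-use hazards are not in the documents; every value below is an assumption for illustration.

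**1. Total dose, equal true daily use in both arms**

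For a window from day a to day b, a participant leaving on day t is observed for the share max(0, min(t, b) − a)/(b − a). Let f be the mean share among leavers and d the proportion leaving. The arm's mean total, relative to full follow-up, is (1 − d) + d·f. The ratio of the higher-dropout arm to the other is [(1 − d2) + d2·f]/[(1 − d1) + d1·f].

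With 10% vs 20%, all leaving at Day 270:

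- Baseline to Day 270: f = 1, ratio 1.000.
- Baseline to Day 365: f = 270/365 = 0.740, ratio (0.8 + 0.2 × 0.740)/(0.9 + 0.1 × 0.740) = 0.973, or 2.7% too low.
- Day 270 to Day 365, leavers scored as zero: f = 0, ratio 0.8/0.9 = 0.889, or 11% too low. With leavers treated as missing, the ratio is 1.000.

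Other patterns, using main-study data from baseline and scoring leavers as zero where they have no days in a window:

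| Dropout | Baseline–270 | Baseline–365 | 270–365 |
|---|---|---|---|
| 10% vs 10%, evenly over Days 180–365 | 1.000 | 1.000 | 1.000 |
| 10% vs 20%, evenly over Days 180–365 | 0.992 | 0.974 | 0.920 |
| 10% vs 20%, all at Day 181 | 0.966 | 0.947 | 0.889 |
| 10% vs 30%, all at Day 181 | 0.932 | 0.894 | 0.778 |

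The baseline windows move less because everyone in ITT has reached Day 180. A Day 181 leaver still contributes 181/270 = 67% and 181/365 = 50% of them.

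If the extension-only scope governs, that cushion goes. With 10% vs 20% all leaving at Day 181, the ratio for Day 180 to Day 270 is 0.890.

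Treating people with no days in a window as missing does not always remove the effect. With 10% vs 20% leaving evenly, 95/185 = 51.35% of leavers go after Day 270 and are observed for half the last window on average. The mean totals are (0.8 + 0.2 × 0.5135 × 0.5)/(0.8 + 0.2 × 0.5135) = 0.943 and (0.9 + 0.1 × 0.5135 × 0.5)/(0.9 + 0.1 × 0.5135) = 0.973. The ratio is 0.969, or 3.1% too low.

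Dividing by days observed gives 1.00 in every case, because daily use was set equal.

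**2. Days to first use, constant hazard h, 365 days, no dropout**

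Share using: p = 1 − e^(−365h). Users-only mean: 1/h − 365·e^(−365h)/p. Median: ln 2/h. Restricted mean over everyone: p/h.

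| h per day | Share using | Users-only mean | Median | Restricted mean |
|---|---|---|---|---|
| 0.01 | 97.4% | 90.3 | 69 | 97.4 |
| 0.002 | 51.8% | 160.5 | 347 | 259.0 |

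The medians differ five-fold; the users-only means differ by 160.5/90.3 = 1.8-fold, with 48% of the second group excluded. A smaller contrast, 0.004 vs 0.002, gives a users-only difference of 160.5 − 139.6 = 20.9 days against a restricted-mean difference of 259.0 − 191.9 = 67.1 days.

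If instead 40% vs 60% use rescue, with the same mean of 60 days among users, the users-only difference is 0. The restricted means are 0.4 × 60 + 0.6 × 365 = 243 and 0.6 × 60 + 0.4 × 365 = 182 days, a difference of 61.

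**The case against.** The strongest reply is that these are untested descriptive tables under safety, while the protocol's per-day measure is an efficacy endpoint that belongs in SAP 12.5.4. That section is in the SAP contents but its text is redacted. SAP 10.6.2, which covers secondary and exploratory efficacy, sets a missing-data rule for rescue use, so an analysis there is plausible. This stands. A reader might infer that the SAP has replaced mean daily use with total dose; the visible text does not support that.

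A reader might also infer that non-users are removed from the rescue comparison. They are not. They are left out of days to first use only, and the SAP says so openly. They remain in the percentage taking acetaminophen and, because the total is for each participant, in the dose summaries. In the 0.01 vs 0.002 example, the 97% vs 52% contrast in use would appear in the same section.

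The 11% needs leavers to enter the last window as zero. Since missing rescue use is not imputed, one can argue that they should be missing there instead. That reading is fair. It shows that the rule is unstated rather than that the totals are sound, because those who leave inside the window still bring truncated totals.

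Finally, the truncation from dropout does not arise in PP, which requires the Day 365 Visit. That is correct, but PP is selected on completion and cannot stand in for the ITT table.

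**Conclusion.** The point holds in a narrow form. As written, the ITT totals in SAP 12.6.6 depend on length of follow-up, and days to first use is conditional on use. Totals distort the arm contrast only if dropout differs between arms in rate or timing, or is related to use; with equal dropout of the same timing and equal daily use there is no distortion.

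Under the assumed 10% vs 20% patterns, the higher-dropout arm is too low by 0 to 3.4% for baseline to Day 270, by 2.6 to 5.3% for baseline to Day 365, and by up to 11% for Day 270 to Day 365, depending on how leavers are scored. The timing statistic can shrink a real difference, or show none when the arms differ in how many people use rescue at all.

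It would go too far to say that rescue use is the plan's main safeguard for the pain result. The documents give it no such role; they list it as exploratory. With descriptive tables and a possible per-day analysis in the redacted text, this is a low-severity improvement.

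**What to change.** In SAP 12.6.6:

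1. Report mean daily dose for each window: total dose divided by days with eDiary data in that window, with non-users as zero. This matches the per-day form of the protocol endpoint. Define a diary day, so that a day of no use is distinguished from a day with no record, and report the days observed by arm.
2. State that a participant with no diary days in a window is missing for that window, not zero.
3. Replace the users-only days-to-first-use summary with a Kaplan-Meier summary by arm, censoring non-users at their last diary day and stating the time origin. Keep the incidence rows.
4. Reconcile the windows that start at main-study baseline with the extension-only data scope in SAP 12.6.
5. If 12.5.4 already specifies mean daily use, cross-refer to it and use the same definition.

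The cost is two changed table shells and a few sentences of text. No new data are needed.

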13.0 References

See Section 11 in trial protocol.

14.0 LIST OF ABBREVIATIONS

AE	adverse event
AESI	adverse event of special interest
AIC	Akaike information criterion
ADPS	Average Daily Pain Score
BPI-DPN	Brief Pain Inventory for Diabetic Peripheral Neuropathy
CDRC	Clinical Data Review Committee
CRO	Clinical Research Organization
CS	clinically significant
CSR	clinical study report
DPN	diabetic peripheral neuropathy
DSMB	Data Safety Monitoring Board
ECG	electrocardiogram
HEENT	head, eyes, ears, nose, and throat
HGF	hepatocyte growth factor
IDMC	Independent Data Monitoring Committee
IM	intramuscular
IRB	Institutional Review Board
ISR	injection site reaction
ITT	intent-to-treat
mITT	modified intent-to-treat
MCMC	Markov Chain Monte Carlo
MedDRA	Medical Dictionary for Regulatory Affairs
MOTH	Mean of the Other Group
MNSI	Michigan Neuropathy Screening Instrument
NCS	not clinically significant
PGIC	Patients' Global Impression of Change
PP	per protocol
SOC	System Organ Class
TEAE	treatment-emergent adverse event
WHODrug	World Health Organization Drug Dictionary
